- Biomarkers measured in plasma (eg, cfDNA) that correlate with response or toxicity to DS-1205c in combination with gefitinib will be assessed.
- EGFR mutation(s) or mutations in other genes in cfDNA during treatment with DS-1205c in combination with gefitinib will be assessed.
- To assess change-from-baseline QTcF (Δ QTcF) when DS-1205c is administered alone or in combination with gefitinib.

CCI

CCI

Planned Sample Size:

Dose Escalation

Approximately 18 subjects will be enrolled.

CCI

Statistical Analyses:

The final efficacy analysis will occur after all subjects have either discontinued the study or completed last study visit or contact.

Safety Analyses:

The safety profile will be based on SAEs, TEAEs, Aes, standard clinical laboratory measurements, vital sign measurements, ECG parameters, physical examination findings, ECHO/MUGA findings, and ophthalmologic findings. Aes and abnormal laboratory values will be graded according to the NCI-CTCAE version 5.0.

Safety analyses in general will be descriptive and will be presented in tabular format with the appropriate summary statistics. In Dose Escalation, the number of DLTs identified among the DLT-evaluable subjects in the DLT-evaluable set will be listed and summarized.

Clinical interpretation of ECGs will be summarized descriptively.

Pharmacokinetic (PK) Analyses:

PK parameters for each subject will be estimated using non-compartmental analysis (NCA). Descriptive statistics will be provided for all plasma concentration

data by analyte/dose/study day/time and for each PK parameter by analyte/dose/study day, as appropriate.

Efficacy Analyses:

The efficacy analysis will be performed for the subjects who received at least one dose of study drug by dose level within each part and overall. The analysis will be based on subjects dosed at the level of RDE at both the dose escalation part and the dose expansion part.

Analyses will be performed for each dose level.

Subjects with unknown or missing response will be treated as non-responders. The estimate of ORR will be reported as a summary statistic. The DCR will be reported as a summary statistic, and point estimates and 2-sided 95% exact binomial confidence intervals (CIs) will be provided. Time to event variables including DOR, TTR, PFS, and OS will be summarized with median event times with 2-sided 95% CI using the Kaplan-Meier method.

Biomarker Analyses:

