6.1.3.10. New Cancer Treatment and Survival Follow-up (Dose Escalation)

After discontinuation from study treatment, follow-up information for survival and subsequent anticancer therapy, if available, should be obtained every 3 months (± 30 days) from the date of the follow-up visit or Safety Follow-up, whichever is later, until death, withdrawal of consent, loss to follow-up, or study closure, whichever occurs first. If direct contacts are not possible due to withdrawal of consent or loss to follow-up, the site must make every effort to collect survival status from public records (eg, death certificates) in accordance with local laws.

[figure not shown]
6.2.

CCI

[figure not shown]

CCI

CCI

CCI

[figure not shown]
CCI

CCI

CCI

CCI

[figure not shown]
CCI

[figure not shown]
CCI

CCI

CCI

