11. STATISTICAL METHODS

11.1. General Statistical Considerations

Descriptive statistics will be provided for selected demographic, safety, PK, and biomarker data from both Dose Escalation and Dose Expansion by dose level within each part and visit as appropriate. Descriptive statistics for continuous data will include means, medians, standard deviations, and minimum and maximum, while categorical data will be summarized using frequency counts and percentages. Graphical summaries of the data may be presented.

Assessments of change from baseline to post-treatment or the ratio of post-treatment to baseline will include only those subjects with both baseline and post-treatment measurements. The last non-missing value of a variable taken before the first dose of study drug will be used as the baseline value, unless otherwise specified. Time-matched baseline will be derived from Cycle 0, Day -1 measurements for all ECG.

Safety analyses will be performed based on the safety analysis sets. Analysis of PK parameters will be based on the PK analysis sets, and biomarker analyses will be based on the PD biomarker analysis sets.

Efficacy endpoints will be analyzed based on the Full Analysis Set (FAS). Data from Dose Escalation will be summarized by dose level within each part and overall.

A detailed statistical analysis plan (SAP) describing the methodology to be used in the final analysis will be prepared and finalized before database lock. Statistical methods described within may be changed based on advances in research.

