11.2. Analysis Sets

- Enrolled Analysis Set will include all subjects who sign the ICF of the study.
- FAS will include all subjects in the Enrolled Analysis Set who received at least one dose of DS-1205c and who had baseline and post-treatment evaluable tumor assessments.
- DLT-Evaluable Set will include subjects enrolled in Dose Escalation who had at least one DLT during the 7 days of Cycle 0 or the 21 days of Cycle 1, or did not have a DLT but received at least 75% of the doses in the 21 days of Cycle 1.
- Safety Analysis Set will include all subjects in the Enrolled Analysis Set, who received at least one dose of DS-1205c. Four groups of subjects will be identified within the Safety Analysis Set: (1) subjects in Dose Escalation, (2) subjects in Dose Expansion, (3) subjects treated at the dose level of RDE, and (4) all treated subjects in the study.
- PK Analysis Set will include all subjects in the Enrolled Analysis Set who received any amount of the study drugs and have sufficient plasma concentration data to characterize PK of DS-1205a or gefitinib.

- Concentration-QTc Analysis Set will include all subjects who are in the Safety Analysis Set with at least one pair of postdose plasma concentration data and QTc data from the same timepoint. The concentration-QTc Analysis Set will be used for the concentration-QTc analysis.
- Biomarker Analysis Set will include all subjects in the Enrolled Analysis Set who received any amount of study drugs and who had the baseline tissue biopsy assessment and, where applicable, at least 1 post-treatment blood sample assessment for biomarkers.

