11.3. Study Population Data

Disposition and reasons for ending the treatment and discontinuing from the study will be summarized and listed for subjects in the Enrolled Analysis Set.

Demographic and baseline characteristics such as age, sex, race, histology, cancer status (metastatic and/or unresectable), molecular mutations (if available), prior treatment regimen(s), best response to prior anticancer treatment(s), will be summarized for the Enrolled Analysis Set, FAS, and Safety Analysis Set. If 2 analysis sets within a part of the study are identical to each other, the table will be presented only once.

Study drug exposure, treatment duration, and compliance with study therapy will be summarized using descriptive statistics for the Safety Analysis Set.

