11.4. Efficacy Analyses

Final data analysis for the clinical study report will occur at the end of the study when all subjects have either completed the End-of-Study Follow-up or discontinued from the study or have received at least 6 months of therapy.

Efficacy endpoints will include ORR (the number of subjects with best objective response [CR or PR], divided by the number of subjects in the analysis population), DOR, DCR (the sum of CR rate, PR rate, and SD rate), TTR, PFS, and OS. CR includes both confirmed CR and unconfirmed CR. Tumor responses will be assessed by an Investigator according to RECIST version 1.1 (Section 17.2).

The efficacy endpoints will be listed and summarized using descriptive statistics based on the FAS by dose level within each part and overall. Study data will be analyzed and reported based on all subjects' data from Dose Escalation and Dose Expansion up until the time when all subjects have potentially completed at least 6 cycles of treatment. Analyses will be performed for each dose level.

The ORR will be based on Investigator's assessments. The analysis will be based on subjects dosed at the level of RDE at both the dose escalation part and the dose expansion part. Subjects with unknown or missing response will be treated as non-responders. Point estimates and 2-sided 95% exact binomial confidence intervals (CIs) will be provided

DOR (the time from documentation of tumor response [either CR or PR] to disease progression) will be based on Investigator's assessments. The DOR will be summarized with median event times with 2-sided 95% CI using the Kaplan-Meier method.

DCR will be reported as a summary statistic by dose cohort. Point estimates and 2-sided 95% exact binomial CIs will be provided.

Time-to-event variables including PFS, TTR, and OS will be summarized with median event times with 2-sided 95% CI using the Kaplan-Meier method. PFS is defined as the time from the date of the first dose to the earlier of the dates of the first objective documentation of radiographic PD or death due to any cause. Censoring rules for the time to event endpoints such as PFS analysis will be specified in the SAP.

Descriptive statistics for the best percentage change from baseline in the sum diameters of measurable tumors will be provided. A waterfall plot of the best percentage change in the sum of diameter for each subject will be presented. In addition, sensitivity analyses will be performed to include confirmed CR only.

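### Section 11 analyses every efficacy endpoint, including PFS and OS, only in dosed subjects with an evaluable post-treatment scan, whereas the synopsis uses all dosed subjects

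*Combined protocol and SAP*

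**What the plan says.** The protocol defines the efficacy population in two ways.

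- **Synopsis, Efficacy Analyses:** "The efficacy analysis will be performed for the subjects who received at least one dose of study drug". ORR, DCR, DOR, TTR, PFS and OS all follow under that heading. There is no scan condition and no mention of the FAS.
- **Section 11.2:** the FAS is restricted to enrolled subjects "who received at least one dose of DS-1205c and who had baseline and post-treatment evaluable tumor assessments".
- **Sections 11.1 and 11.4:** efficacy endpoints are analysed on the FAS. Section 11.4 lists OS among them and assigns no endpoint to another set.

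The synopsis and Section 11.4 share the same rule for missing data: "Subjects with unknown or missing response will be treated as non-responders".

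Section 7.1.1 measures OS from the first dose of DS-1205c to death from any cause, and counts death from any cause as a PFS event. After a subject stops treatment, Section 6.1.3.10 states that "follow-up information for survival and subsequent anticancer therapy, if available, should be obtained every 3 months", and Section 5.6.1 likewise provides for survival follow-up. In Section 11.2 a population defined by dosing alone appears only as the Safety Analysis Set.

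**The concern.** The two populations differ by exactly the dosed subjects who have no evaluable pair of baseline and post-treatment tumor assessments. Those most clearly affected are subjects who die or withdraw before any evaluable post-treatment scan.

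Three things follow from Section 11 as written:

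- For ORR and DCR, these subjects leave the denominator before the missing-response rule can reach them. The rule then covers only FAS members whose response is unknown. Under the synopsis it would also cover treated subjects who were never scanned.
- For PFS and OS, an unscanned early death is removed altogether, although OS needs no scan and the protocol collects survival after discontinuation. Entry to the analysis depends on living long enough to be scanned, while the clock starts at first dose. This is guarantee-time bias.
- The trial has no comparator, so nothing within it would offset the shift.

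**Working it through.** The plan states no efficacy figure that depends on the population, so there is nothing to reproduce. The text comparison above settles the conflict. The wording *study drug* against *DS-1205c* does not explain it: the synopsis names DS-1205c as the study drug, and in Dose Escalation it is given first and alone in Cycle 0. The calculations below only illustrate size. The share of unscanned subjects is not in the documents.

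**Response rates.** Let n be the number dosed, k the number without an evaluable scan, and f = k/n. The excluded subjects have neither response nor disease control, so the numerator is unchanged and the estimate is multiplied by n/(n − k) = 1/(1 − f). That is 1.05, 1.11 and 1.18 for f = 5%, 10% and 15%. With a numerator of zero nothing changes.

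Using the roughly 18 planned escalation subjects, assumed counts, and the exact binomial intervals that Section 11.4 specifies:

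- ORR 3/18 = 16.7% (3.6 to 41.4) becomes 3/17 = 17.6%, 3/16 = 18.8% or 3/15 = 20.0% (4.3 to 48.1).
- DCR 9/18 = 50.0% (26.0 to 74.0) becomes 9/15 = 60.0% (32.3 to 83.7).
- At one dose level with 6 dosed (the minimum at the selected dose, Section 11.9), 2/6 = 33.3% (4.3 to 77.7) becomes 2/5 = 40.0% (5.3 to 85.3).

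DOR is unaffected, because a responder must have an evaluable scan.

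**OS in Dose Escalation.** Inputs:

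- First scheduled scan: 7 days of Cycle 0 plus 6 weeks from Cycle 1 Day 1 = 7 + 42 = day 49 after first dose, or day 42 to 56 with the 7-day window (Sections 3.2.1.1, 6.1.3.5). Dividing by 30.4375 gives c = 1.38, 1.61 and 1.84 months for days 42, 49 and 56.
- Survival: exponential, S(t) = 0.5^(t/m). This is an assumption. I take m = 10.8 and 28.9 months, the lowest and highest median OS that Section 1.2.1 cites for other regimens.
- q: the assumed share of deaths before c that are unscanned.

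Deaths before day 42, 49 and 56 are 8.5%, 9.8% and 11.1% for m = 10.8, and 3.3%, 3.8% and 4.3% for m = 28.9.

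Removing a share q of the early deaths makes FAS survival after c equal to S(t)/(1 − q(1 − S(c))). The FAS median therefore solves S(t) = 0.5 × (1 − q(1 − S(c))).

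- q = 1: S(t) = 0.5 × S(c), so t = m + c. The shift equals c whatever m is.
- q = 0.5, m = 10.8, day 49: S(c) = 0.902, and 1 − 0.5 × 0.098 = 0.951. The target is S(t) = 0.4755, so t = 10.8 × ln(0.4755)/ln(0.5) = 11.58, a shift of +0.78.

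| Upward shift in median OS (months) | day 42 | day 49 | day 56 |
|---|---|---|---|
| q = 0.5, m = 10.8 | 0.67 | 0.78 | 0.89 |
| q = 0.5, m = 28.9 | 0.68 | 0.80 | 0.91 |
| q = 1, either m | 1.38 | 1.61 | 1.84 |

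**The case against.** **The SAP will settle it.** Section 11.10 says the SAP will supply definitions for the efficacy analysis and describe how missing data are handled. That gives a natural place to resolve the point. It is a general deferral, though, and it does not say which population applies. Unless the protocol is reconciled, any SAP must depart from one of its two statements.

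**The ORR paragraph may already mean all dosed subjects.** Section 11.4 bases the ORR analysis on subjects dosed at the RDE and then applies the missing-response rule. This could be an all-dosed denominator, or only a dose-level filter within the FAS. The ambiguity stands for ORR. It does not help PFS or OS, where the conflict is cleanest.

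**Few subjects may be lost.** Entry requires ECOG 0 or 1 without recent deterioration. Unscheduled scans are allowed on suspected progression, an end-of-treatment scan is planned, and Section 17.2.2.4.4 asks for progression to be documented after discontinuation. These provisions keep some early failures in the FAS. The OS shift that assumes every early death is unscanned is therefore an upper-end figure for deaths.

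**The counts will be visible.** Baseline data "will be summarized for the Enrolled Analysis Set, FAS, and Safety Analysis Set", so a reader could infer how many were excluded. The estimates would still be uncorrected.

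A reader might also infer more than the documents support:

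- *That subjects who stop early for toxicity are excluded through the end-of-treatment scan waiver.* This needs the waiver's previous scan to include the screening scan, and scanning to end at discontinuation. Sections 6.1.3.8, 7.1.1 and 17.2.2.4.5 settle neither.
- *That survival at the reporting point, "up until the time when all subjects have potentially completed at least 6 cycles of treatment", would be overstated by a definite amount.* The plan calls for Kaplan-Meier medians, not a landmark survival estimate.
- *That the day-49 timing holds throughout the trial.* Cycle 0 exists only in Dose Escalation.

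**Conclusion.** The conflict is real and should be corrected. Followed literally, Section 11 drops unscanned early deaths from PFS and OS, and it can only leave ORR and DCR unchanged or raise them.

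The likely size is modest. The response shifts are small against the exact intervals. For Dose Escalation, median OS would be about 0.7 to 0.9 months too high if half of the deaths before the first scheduled scan are unscanned, and 1.4 to 1.8 months if all are. These figures rest on exponential survival, assumed counts and an assumed unscanned share. They are not bounds on the total effect, because subjects excluded while alive could move OS in either direction. It would therefore be wrong to read them as a guaranteed upward bias in OS.

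It would also go too far to infer that dose decisions are compromised. DLT evaluation does not use the FAS, and Section 3.2.1.6 draws on all available tumor response data for the RDE. In the visible text, efficacy in Dose Escalation is secondary and descriptive. The same cannot be asserted for Dose Expansion, whose objectives, endpoints and sample size are redacted, although Section 11.4 bases the ORR analysis on RDE-level subjects from both parts.

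**What to change.** In Section 11.2, define the FAS as all subjects who received at least one dose of DS-1205c, in line with the synopsis, and use it for ORR, DCR, PFS and OS. Then:

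- count subjects with no post-baseline scan as non-responders and as not having disease control;
- keep them in PFS and OS, with the PFS censoring rules that Section 11.4 already leaves to the SAP;
- rename the scan-based set as response-evaluable, and use it only for a supportive ORR and the waterfall plot. Section 11.1 already says that change-from-baseline assessments "will include only those subjects with both baseline and post-treatment measurements", so the FAS does not need the scan condition for that purpose;
- report by dose level how many treated subjects had no post-baseline scan.

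The cost is a one-sentence change in Section 11.2 carried into the SAP, one renamed set, one supportive table and one count. No new data are needed, since survival is already collected. The downside is that ORR and DCR may come out slightly lower.

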11.3. Study Population Data

Disposition and reasons for ending the treatment and discontinuing from the study will be summarized and listed for subjects in the Enrolled Analysis Set.

Demographic and baseline characteristics such as age, sex, race, histology, cancer status (metastatic and/or unresectable), molecular mutations (if available), prior treatment regimen(s), best response to prior anticancer treatment(s), will be summarized for the Enrolled Analysis Set, FAS, and Safety Analysis Set. If 2 analysis sets within a part of the study are identical to each other, the table will be presented only once.

Study drug exposure, treatment duration, and compliance with study therapy will be summarized using descriptive statistics for the Safety Analysis Set.

11.4. Efficacy Analyses

Final data analysis for the clinical study report will occur at the end of the study when all subjects have either completed the End-of-Study Follow-up or discontinued from the study or have received at least 6 months of therapy.

Efficacy endpoints will include ORR (the number of subjects with best objective response [CR or PR], divided by the number of subjects in the analysis population), DOR, DCR (the sum of CR rate, PR rate, and SD rate), TTR, PFS, and OS. CR includes both confirmed CR and unconfirmed CR. Tumor responses will be assessed by an Investigator according to RECIST version 1.1 (Section 17.2).

The efficacy endpoints will be listed and summarized using descriptive statistics based on the FAS by dose level within each part and overall. Study data will be analyzed and reported based on all subjects' data from Dose Escalation and Dose Expansion up until the time when all subjects have potentially completed at least 6 cycles of treatment. Analyses will be performed for each dose level.

The ORR will be based on Investigator's assessments. The analysis will be based on subjects dosed at the level of RDE at both the dose escalation part and the dose expansion part. Subjects with unknown or missing response will be treated as non-responders. Point estimates and 2-sided 95% exact binomial confidence intervals (CIs) will be provided

DOR (the time from documentation of tumor response [either CR or PR] to disease progression) will be based on Investigator's assessments. The DOR will be summarized with median event times with 2-sided 95% CI using the Kaplan-Meier method.

DCR will be reported as a summary statistic by dose cohort. Point estimates and 2-sided 95% exact binomial CIs will be provided.

Time-to-event variables including PFS, TTR, and OS will be summarized with median event times with 2-sided 95% CI using the Kaplan-Meier method. PFS is defined as the time from the date of the first dose to the earlier of the dates of the first objective documentation of radiographic PD or death due to any cause. Censoring rules for the time to event endpoints such as PFS analysis will be specified in the SAP.

Descriptive statistics for the best percentage change from baseline in the sum diameters of measurable tumors will be provided. A waterfall plot of the best percentage change in the sum of diameter for each subject will be presented. In addition, sensitivity analyses will be performed to include confirmed CR only.

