6.1.3.5. Tumor Assessments (Dose Escalation)

- Investigator determined tumor assessments of the chest, abdomen, and pelvis and other areas where scans were performed at screening or newly suspected disease should be performed every 6 weeks (± 7 days) from Cycle 1, Day 1 for the first 24 weeks then every 12 weeks (± 7 days) thereafter. The same methodology (CT or MRI) and scan acquisition techniques (including use or nonuse of IV contrast) as were used for the screening assessments should be used throughout the study for all assessments for each subject unless prior approval is obtained from the Sponsor. Unscheduled tumor assessments may be conducted if progression is suspected. Tumor assessments should not be delayed by dose interruptions; they are timed relative to Cycle 1, Day 1. Tumor assessments should be performed per RECIST version 1.1 (Section 17.2). SpO₂ should also be measured at the time of tumor assessment per Investigator discretion.
- Objective responses must be confirmed at least 4 weeks later (eg, generally at the next tumor assessment time point). Perform CT or MRI of the brain in subjects with baseline brain metastases or if clinically indicated, and within a target of 1 week after a subject achieves a CR. A bone scan (99m-technetium polyphosphonate scintigraphy, whole body bone MRI, or ¹⁸F-NaF) to assess bone metastases should be performed every 24 weeks (within that 24th week)

from C1D1, or sooner if clinically indicated. In subjects whose body CT/MRI scans indicate CR has been achieved, a bone scan will be required at confirmation of CR to exclude new bone metastases. Lesions detected on bone scans must be followed with cross-sectional imaging.

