- m. Obtain three 3 mL samples for pharmacodynamic biomarkers (osteopontin, IL 8, SAXL) pre dose as indicated. As a general rule, blood collection should be conducted after ECG measurement. Refer to the Laboratory Manual for instructions for collection, processing, and shipping of samples.
- n. A bone scan (99m technetium polyphosphonate scintigraphy, whole body bone MRI, or 18F NaF) to assess bone metastases should be performed every 24 weeks (within that 24th week) from C1D1, or sooner if clinically indicated. In subjects whose body CT/MRI scans indicate CR has been achieved, a bone scan should be required at confirmation of CR to exclude new bone metastases. Lesions detected on bone scans must be followed with cross sectional imaging.
- o. The same methodology (CT or MRI) and scan acquisition techniques (including use or nonuse of IV contrast) as were used for the screening assessments should be used throughout the study for all assessments for each subject unless prior approval is obtained from the Sponsor. Unscheduled tumor assessments may be conducted if progression is suspected. Tumor assessments should not be delayed by dose interruptions; they are timed relative to Cycle 1, Day 1. Tumor assessments should be performed per RECIST version 1.1.
- p. Investigator determined tumor assessments of the chest, abdomen, and pelvis and other areas where scans were performed at screening or newly suspected disease should be performed every 6 weeks (\pm 7 days) from Cycle 1, Day 1 for the first 24 weeks then every 12 weeks (\pm 7 days) thereafter. Objective responses must be confirmed at least 4 weeks later (eg, generally at the next tumor assessment time point). Perform CT or MRI of the brain in subjects with baseline brain metastases or if clinically indicated, and within a target of 1 week after a subject achieves a CR.
- q. Perform radiographic tumor assessments (CT/MRI) of the chest, abdomen and pelvis and all sites of disease, as per RECIST version 1.1. If the previous scan was performed within the last 6 weeks, this assessment does not need to be performed at the EOT visit.
- r. Ophthalmologic assessments (visual acuity, slit lamp examination, fundoscopy, and tonometry) should be performed on Day 1 of Cycle 2 (7 days), on Day 1 of Cycle 4 (7 days) and every 4 cycles (7 days) thereafter, and at EOT(7 days). Investigators must ensure results of ophthalmologic assessments are available for review prior to dosing on corresponding cycle visits.

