7. EFFICACY ASSESSMENTS

7.1. Assessments for Efficacy Endpoint(s)

7.1.1. Efficacy Endpoint(s)

Efficacy assessments will be determined at Screening and by follow-up imaging using RECIST version 1.1 (Section 17.2). Tumor assessments should be conducted every 6 weeks (± 7 days) from Cycle 1, Day 1 for the first 24 weeks then every 12 weeks (± 7 days) thereafter, as indicated in the Schedule of Events (Table 6.2, Table 6.3), until radiological progression or until the subject permanently discontinues treatment. The schedule of efficacy assessments is determined relative to Cycle 1, Day 1 and will not be altered by interruptions in treatment. The antitumor activity endpoints will include percentage change in size of target lesion(s), ORR, DOR, DCR, PFS, and OS. ORR is defined as the sum of CR and PR rates. CR includes both confirmed CR (as described in Section 6.1.3.5 and Section 6.2.2.6) and unconfirmed CR. DOR is measured from the time of first CR or first PR until the first date of PD. TTR is measured from the date of first dose of DS-1205c to first objective response (CR or PR). DCR is the sum of CR rate, PR rate, and SD rate. PFS is defined as the time from the date of first dose of DS-1205c to the earliest date of the first objective documentation of radiographic disease progression per RECIST Version 1.1 or death due to any cause. OS is defined as from the date of first dose of DS-1205c to death due to any cause.

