17.2.2.4.3. Best Overall Response: All Time Points

Best response determination in trials where confirmation of CR or PR is required: When SD is believed to be best response, it must also meet the protocol-specified minimum time from baseline, 6 weeks. If the minimum time is not met when SD is otherwise the best time point response, the subject's best response depends on the subsequent assessments. CR or PR may be claimed only if the criteria for each are met at a subsequent time point as specified in the protocol. In this circumstance, the best overall response can be interpreted as in [Table 17.2](#).

Table 17.2: Best Overall Response When Confirmation of CR and PR Is Required

Overall Response, First Time Point	Overall Response, Subsequent Time Point	Best Overall Response
CR	CR	CR
CR	PR	SD, PD or PR ^a
CR	SD	SD provided minimum criteria for SD duration met otherwise, PD
CR	PD	SD provided minimum criteria for SD duration met otherwise, PD
CR	NE	SD provided minimum criteria for SD duration met otherwise, NE
PR	CR	PR
PR	PR	PR
PR	SD	SD
PR	PD	SD provided minimum criteria for SD duration met otherwise, PD
PR	NE	SD provided minimum criteria for SD duration met otherwise, NE
NE	NE	NE

CR = complete response, PR = partial response, SD = stable disease, PD = progressive disease, and NE = not evaluable.

If a CR is truly met at first time point, then any disease seen at a subsequent time point, even disease meeting PR criteria relative to baseline, makes the disease PD at that point (since disease must have reappeared after CR). Best response would depend on whether minimum duration for SD (6 weeks) was met. However, sometimes ‘CR’ may be claimed when subsequent scans suggest small lesions were likely still present and in fact the subject had PR, not CR at the first time point. Under these circumstances, the original CR should be changed to PR and the best response is PR.

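### The main ORR counts unconfirmed CRs although the protocol's own response rules require CR and PR to be confirmed, and the protocol's DOR definition has no event for death

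*Combined protocol and SAP*

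**What the plan says.** **Counting rule for the analysis.** Section 11.4 says "CR includes both confirmed CR and unconfirmed CR". Section 7.1.1 says the same and points to the tumor-assessment section for what confirmed means: "CR includes both confirmed CR (as described in Section 6.1.3.5 and Section 6.2.2.6) and unconfirmed CR". Neither section says whether an unconfirmed PR counts. Section 11.4 adds a sensitivity analysis restricted to confirmed CR.

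**Rule for calling a response.** Section 6.1.3.5 says "Objective responses must be confirmed at least 4 weeks later (eg, generally at the next tumor assessment time point"). Table 6.2 footnote p (Section 6.3) repeats it: "Objective responses must be confirmed at least 4 weeks later". Section 17.2.2.4.3 says "CR or PR may be claimed only if the criteria for each are met at a subsequent time point as specified in the protocol", and Table 17.2 is the version of the best-overall-response table for trials that require confirmation. Section 11.4 names Section 17.2 as the standard for response assessment.

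**DOR.** The synopsis and Sections 2.3.1, 7.1.1 and 11.4 all run DOR from first response to progression. None mentions death. PFS, in 7.1.1 and 11.4, ends at radiographic PD or death from any cause. Section 11.4 leaves censoring rules to the SAP, and Section 11.10 leaves efficacy definitions to it as well.

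**The concern.** Two instructions that both apply to the same analysis give different answers for the same subject. A programmer who follows 11.4 counts a CR that vanishes at the next scan as a response; one who follows Table 17.2 does not. Responder status also decides who enters DOR and which date ends time to response (TTR), so the ambiguity carries into both.

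For DOR, the stated endpoint gives no event to a responder who dies before progression is documented. The plan makes such deaths plausible. Section 5.6.1 allows withdrawal for clinical progression that does not meet RECIST PD, and Section 7.1.1 ends scheduled scans at permanent treatment discontinuation. Survival follow-up continues every 3 months (Section 6.1.3.10). If these deaths are censored, the DOR curve cannot be lower than the curve that counts them, and it will usually be higher.

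The study is open-label with investigator-assessed response, and tumor response is one of the inputs to the recommended dose for expansion (RDE; Section 3.2.1.6). The counting rule should be settled before responses are known.

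**Working it through.** The documents give no power, sample-size or event figure that depends on either definition, so there is no plan figure to reproduce. The check sets the rules side by side and then sizes a single reclassification.

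**1. Same scan sequence, two rules**

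| First, then next assessment | Sections 7.1.1 / 11.4 | Table 17.2 |
|---|---|---|
| CR, CR | response | CR |
| CR, PR | response | SD, PD or PR; a response if re-read as PR |
| CR, SD | response | "SD provided minimum criteria for SD duration met otherwise, PD" |
| CR, PD | response | SD or PD, by the same condition |
| CR, NE | response | SD if the minimum duration is met, otherwise NE |
| PR, PD | not stated | SD or PD, by the same condition |
| PR, NE | not stated | SD if the minimum duration is met, otherwise NE |

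The rules disagree for CR followed by SD, PD or NE. For CR followed by PR the footnote offers a way out: if small lesions were probably present all along, "the original CR should be changed to PR and the best response is PR", and the subject stays a responder. For PR, Table 17.2 is the only rule given, and it downgrades an unconfirmed PR. Read together, CR then PD counts as a response and PR then PD does not.

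**2. What a downgraded CR becomes.** Section 17.2.2.4.3 says "When SD is believed to be best response, it must also meet the protocol-specified minimum time from baseline, 6 weeks". In Dose Escalation, Cycle 0 lasts 7 days and the first scan is due 6 weeks (42 days) after Cycle 1, Day 1, with a window of ±7 days. The earliest on-schedule scan after the first DS-1205c dose is 7 + 42 − 7 = 42 days = 6 weeks. The SD minimum is met, so the downgraded CR becomes SD: ORR falls and the disease control rate does not change. An unscheduled early scan could break this.

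**3. Size of one reclassification.** The change in ORR is 1/n. The values of n are illustrative: 3 is the minimum DLT-evaluable number per dose level, 6 the minimum at the selected dose and 18 the minimum in total (Sections 3.2.1.5 and 11.9). The intervals are Clopper-Pearson 95%, matching the exact method in 11.4. The responder counts are assumed.

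| n | With the unconfirmed CR | Without it | Change |
|---|---|---|---|
| 3 | 1/3 = 33.3% (0.8 to 90.6) | 0/3 = 0% (0 to 70.8) | 33.3 points |
| 6 | 2/6 = 33.3% (4.3 to 77.7) | 1/6 = 16.7% (0.4 to 64.1) | 16.7 points |
| 18 | 4/18 = 22.2% (6.4 to 47.6) | 3/18 = 16.7% (3.6 to 41.4) | 5.6 points |

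The Full Analysis Set (Section 11.2) may differ from these numbers. The RDE-level ORR also pools Dose Expansion, whose size is redacted.

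**4. DOR with deaths censored.** Assume constant hazards, and let f be the share of first events that are deaths without PD. With total hazard λ, the median is ln 2/λ if deaths count and ln 2/[λ(1 − f)] if they are censored. The ratio is 1/(1 − f).

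| Assumed f | Ratio of medians |
|---|---|
| 5% | 1.05 |
| 10% | 1.11 |
| 20% | 1.25 |
| 30% | 1.43 |

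The documents give no value for f.

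**5. Do the planned scans allow confirmation?** The shortest gap between on-schedule scans is 42 − 7 − 7 = 28 days in the first 24 weeks and 84 − 7 − 7 = 70 days after that. Both meet the 4-week requirement.

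**The case against.** **Counting unconfirmed CR is openly stated, and a confirmed-CR analysis is already planned.** For CR, then, both results should be reported, and which one leads a descriptive Phase 1 secondary endpoint is partly a matter of preference. This lowers the stakes but leaves the conflict. Section 11.4 departs from the criteria it cites and gives no reason. The sensitivity sentence names no endpoint and does not mention PR.

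**The different treatment of CR and PR is inferred.** This is fair. Sections 7.1.1 and 11.4 are silent on unconfirmed PR, and the asymmetry appears only when they are read with Table 17.2. The silence itself needs filling.

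**The SAP may define DOR differently.** This also stands. Section 11.10 defers efficacy definitions as well as censoring rules, and the combined document contains no separate SAP text that settles the matter. A reader might infer that deaths will be censored and DOR inflated. The documents support only the conditional statement. A DOR that ends at progression is also a different quantity, not in itself an error; it is overstated only relative to a PD-or-death definition consistent with PFS.

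**A reader might infer that the data cutoff will itself produce unconfirmed CRs.** Section 11.4 mentions reporting once all subjects could have completed 6 cycles (6 × 21 = 126 days, or 18 weeks), which would leave a CR first seen at week 18 without a later scan. The documents do not support building on that. The same section also places the final analysis at completed follow-up, discontinuation or at least 6 months of therapy, and the synopsis places it after all subjects have discontinued or completed their last visit or contact.

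**Conclusion.** The point holds on the text. Sections 7.1.1 and 11.4 contradict Section 6.1.3.5, Table 6.2 footnote p and Table 17.2 on whether an unconfirmed CR is a response, and they leave unconfirmed PR undefined. The DOR gap is certain for the protocol definition and conditional for the analysis, because the SAP may still change it.

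The plan should be corrected here, but nothing in the visible design turns on it. ORR and DOR are descriptive secondary endpoints in Dose Escalation, with no visible test, threshold or sample size attached. RDE determination is guided by the DLT-based model, with response as one input among several. The 1/n shifts and the 1/(1 − f) ratios show what one subject or an assumed share of deaths would do; they are not forecasts. Only CRs that are never confirmed and not re-read as PR are affected by the ORR conflict, and the documents give no basis for saying how many there will be.

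**What to change.** In Sections 7.1.1 and 11.4 and in the SAP:

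- Define best overall response and the main ORR as confirmed CR or confirmed PR, following Section 6.1.3.5 and Table 17.2.
- Report confirmed plus unconfirmed CR and PR as the sensitivity analysis for ORR, DOR and TTR.
- State that a CR or PR first seen at the last scan before data cutoff counts as unconfirmed.
- Define DOR, among confirmed responders, from the first CR or PR (later confirmed) to the earlier of PD or death from any cause, and carry the same definition into the synopsis and Section 2.3.1. Put its censoring rules beside those for PFS.

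**Cost.** The change is wording. Subjects who stay on schedule need no extra scan, and survival data are already collected.

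**Downside.** ORR may be slightly lower. Responses first seen at the last scan before cutoff leave the main ORR. So do responders who stop treatment and scanning before a confirmatory scan: Section 7.1.1 ends scans at permanent discontinuation, and Section 6.1.3.8 waives the end-of-treatment scan if one was done within 6 weeks. Section 17.2.2.4.5 reads differently on how long scanning continues, so these passages should be reconciled at the same time. DOR may move in either direction, because dropping unconfirmed responses tends to lengthen it and counting deaths shortens it.
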